# 12.2. Objective Findings

Any clinically significant changes from signing of the ICF in objective findings (eg, clinical laboratory value, ECG value, vital sign values and physical / neurological examination observation), as determined by the Investigator, will be recorded as AEs.

When a clear diagnosis is available that explains the objective findings, this diagnosis will be recorded as the AE, and not the abnormal objective finding (eg, viral hepatitis will be recorded as the AE, not transaminase elevation). If a definite diagnosis is not available, then record the sign (eg, clinically significant elevation of transaminase levels) or symptom (eg, abdominal pain) as the AE.

Clinical laboratory test results and ECG tracings and over-read reports will be reviewed, signed and dated by the Investigator. The Investigator must determine the clinical significance of all out-of-range values for clinical laboratory tests and all abnormal ECG findings.

Any clinical laboratory value outside the normal range and any centrally over-read abnormal ECG finding will be flagged for the attention of the Investigator or appropriate designee at the study center. The Investigator or appropriate designee will indicate whether the value/finding is of clinical significance. If a clinically significant laboratory or ECG abnormality is found during the study, and/or at the Follow-Up Visit, this should be recorded as an AE and the subject will be followed until the test(s) has (have) normalised or stabilised. Possibly drug-related or clinically relevant abnormal values of uncertain causality or clinical significance must be repeated. Additional laboratory and ECG testing during the study may be performed if medically indicated.

# 12.3. Collection and Recording of Adverse Events

All pre-treatment events and AEs must be recorded in the subject's study records/source documents in accordance with the Investigator's normal clinical practice. Pre-treatment events and AEs and SAEs that occur from the signing of informed consent to the subject's last study visit must be recorded on the CRF. Determination of whether an event is a pre-treatment event, or an adverse event will be made programmatically by the Sponsor or designee, not by the site.

All AEs will be followed until resolution, stabilization of the condition, the event is otherwise explained, or the subject is lost to follow-up.

Each AE is to be evaluated for duration, severity, frequency, seriousness, action taken with the study treatment, outcome, and causal relationship to the study treatment. Additional information will be collected for the non-serious psychiatric AEs that led to discontinuation from the study as well as all serious psychiatric AEs within the study. Definitions for severity, frequency, action taken with the study treatment, outcome, and causal relationship to the study treatment are presented below.

# The severity of AE:

- **Mild** Ordinarily transient symptoms that do not influence performance of subject's daily activities. Other treatment is not ordinarily indicated.
- **Moderate** Marked symptoms sufficient to make the subject uncomfortable. Moderate influence on performance of subject's daily activities. Other treatment may be necessary.
- **Severe** Symptoms cause considerable discomfort. Substantial influence on subject's daily activities. May be unable to continue the study, and other treatment may be necessary.

#### The frequency of AE:

- Once an isolated episode.
- Intermittent occurs on two or more separate occasions.
- Continuous does not abate from date of onset to date of resolution.

The action taken with the study treatment:

- **Drug Interrupted** Study drug stopped temporarily.
- **Drug Withdrawn** Study drug stopped permanently.
- Dose Reduced
- Dose Increased
- Dose Not Changed
- Not Applicable
- Unknown

#### The outcome of the AE:

- Recovered/Resolved
- Recovering/Resolving
- Not Recovered/Not Resolved
- Recovered/Resolved with Sequelae
- Fatal
- Unknown

The causal relationship of the AE to the study treatment:

#### • Not related

• **Not related** - Improbable temporal relationship and is plausibly related to other drugs or underlying disease.

#### Related

- **Possible** occurred in a reasonable time after study drug administration but could be related to concurrent drugs or underlying disease.
- o **Probable** occurred in a reasonable time after study drug administration, is unlikely to be attributable to concurrent drugs or underlying disease, and there is a plausible mechanism to implicate the study drug.
- O **Definite** occurred in a reasonable time after study drug administration and cannot be explained by concurrent drugs or underlying disease. The adverse event should respond to dechallenge/rechallenge; however, this is not mandatory before assigning a definite causality.

The Medical Monitor is the initial contact person for protocol related questions or discussion of AEs. The contact information for the Medical Monitor as well as other emergency contact information can be found in Table 1 of this protocol.

# 12.4. Immediately Reportable Events

The following medical events must be immediately reported to the Sponsor:

- SAE
- Pregnancy

Emergency contact information can be found in Table 1.

#### 12.4.1. Serious Adverse Event

If the Investigator or study center staff becomes aware of a SAE that occurs in a study subject after first administration of study drug through 30 days following the last dose of the study drug, this must be reported immediately to the Sponsor whether considered related or unrelated to the study drug. SAEs that occur from the signing of the ICF up to the last visit must be recorded on the CRF and the data recorded should agree with those on the SAE form. In addition, pretreatment events that meet the definition of serious (Section 12.1.2) should be reported following the same guidelines.

Should the Investigator become aware of an SAE greater than 30 days post last dose, the Investigator or an authorized delegate should report SAEs "spontaneously" to PPD-PVG if considered at least possibly related to the study drug.

SAEs will be followed until resolution, loss to follow-up, stabilization of condition, or the event is otherwise explained.

An initial or follow-up SAE form as applicable must be completed and signed and sent via fax or email (see Table 1) to PPD-PVG immediately but not more than 24 hours after the Investigator

or study center staff become aware of the event. Response to specific questions included on the SAE form for psychiatric SAEs is required. The SAE form must be signed by the Investigator or appropriate designee. The Sponsor provides the SAE form used to report SAEs.

The Sponsor or designee will promptly notify all study centers and Investigators of an SAE that is determined to be expedited to the Regulatory Authorities in accordance with applicable law(s) and regulation(s). These SAEs must be promptly reported to the Institutional Review Board (IRB) or Independent Ethics Committee (IEC) by the Investigator or the appropriate person at the study center if required per IRB/IEC guidelines.

# 12.4.2. Pregnancy

Pregnancies that occur from the time that informed consent is signed through 90 days following the last dose of the study medication will be collected and reported on the Pregnancy Event Form.

If a subject becomes pregnant during the course of the study, she will be instructed to stop taking the study medication. Further, the subject will be instructed to return to the study center within 48 hours of the first notification of pregnancy and undergo a serum pregnancy test, as confirmation of pregnancy. If positive, the female pregnant subject will no longer receive any additional study medication. All pregnancies, whether or not the subject received any additional study medication, will be followed until resolution (ie, termination [voluntary or spontaneous] or birth). Infants may be followed for up to one year following birth.

If a pregnancy is reported for a study subject's partner from time of subject's first dose to 30 days post last dose, the subject's partner may be asked to sign a consent form to allow the Sponsor to follow her pregnancy. The Sponsor's representative will provide instructions on how to collect pregnancy information in accordance with local requirements. Proper consent to collect the partner's information will be obtained before the collection of any information.

To report a pregnancy, the Pregnancy Event Form must be completed and sent via fax to PPD-PVG immediately but no more than 24 hours after the Investigator or study center staff becomes aware of the pregnancy. The Sponsor provides the Pregnancy Event Form.

Pregnancy itself is not regarded as an AE unless there is a suspicion that the study drug may have interfered with the effectiveness of a contraceptive medication or other AEs were detected.

#### 13. TERMINATION OF SUBJECT FROM STUDY

# **13.1.** Criteria for Subject Termination

Subjects may be discontinued from study participation / the study drug at any time for any of the following reasons. The possible reasons for termination of study participation / study drug are as follows:

- Adverse event
- Lack of efficacy (specify)
- Lost to follow-up (specify)
- Withdrawal by subject (specify)
- Non-compliance with study drug (specify)
- Protocol deviation (specify)
- Death
- Pregnancy
- Other (specify)

If at any time during the course of the study, in the opinion of the Investigator, the subject may no longer safely participate due to a change in medical status (eg, experiences an AE, becomes pregnant), the subject must be discontinued from the study drug. Subjects discontinued from study drug will be discontinued from the study.

The reason for discontinuation of "Lack of efficacy" should be selected when a subject early terminates from the study because there has been insufficient therapeutic benefit of the study drug (perceived or actual) and the subject's baseline condition has neither worsened nor improved significantly.

The reason for study drug discontinuation will be recorded on the appropriate CRF. In case of death, the date of death should be captured on the CRF. Subjects who prematurely terminate the study participation will not be replaced.

# 13.2. Clinical Assessments After Study Drug Discontinuation

Subjects who have not received any study drug will not be followed up on leaving the study.

For subjects who have received study drug and who prematurely discontinue from the study treatment (ie, do not complete through Week 24), every effort should be made to complete the final evaluation procedures, in accordance with the ET visit described in Section 11.6.7.

Subjects who complete the study and those subjects who discontinue the study early will complete a follow up visit 7 (±2) days after the last dose of study drug as described in Section 11.6.9.

# 14. STUDY TERMINATION

The Sponsor reserves the right to discontinue the study at this study center or at multiple centers for safety or administrative reasons at any time while safeguarding that early termination does not compromise subjects' safety or well-being. In particular, a study center that does not recruit at an acceptable rate may be closed. Should the study be terminated, and/or the study center closed for whatever reason, all documentation and study medication pertaining to the study must be returned to the Sponsor or its representative.

If, in the opinion of the Investigator, clinical observations suggest it may be unsafe to continue, the Investigator may terminate part of the entire study after consultation with the Sponsor.

In the event of study or site termination, subjects will undergo final evaluation procedures in accordance with the early termination (ET) visit described in Section 11.6.7 and safety Follow-up Visit as described in Section 11.6.9.

#### 15. STATISTICS

The Statistical Analysis Plan (SAP) will provide the details on the statistical methods planned for this study and will be finalized before the database lock of the study.

# 15.1. Sample Size

All subjects who complete SEP361-308 are eligible to enroll. It is anticipated that approximately 67 subjects will enroll in this study (SEP361-309), assuming 75% of the subjects complete Study SEP361-308 and 75% of the completers will enroll in this study. The sample size is not based on statistical considerations.

# 15.2. Analysis Populations

# **15.2.1.** Safety Population

The safety population will consist of all subjects who receive at least one dose of study drug during the 24-week OLE treatment period. The Safety Population will be used for the long-term safety, tolerability, and effectiveness analyses.

# 15.3. Data Analysis

Descriptive statistics will be compiled for all endpoints for the overall treatment group.

# 15.3.1. Subject Disposition

Subject disposition will be summarized and presented for the number and percentage of subjects who entered the extension study, received at least one dose of the open-label extension study drug, and completed or discontinued from the open-label extension treatment period (including reasons for discontinuation).

## 15.3.2. Study Drug Exposure and Compliance

Duration of exposure and compliance during the open-label extension treatment period will be summarized for the safety population.

Duration of exposure (in days) will be calculated as: last extension study dose date - first extension study dose date + 1. Duration of exposure will be summarized both as a continuous variable and categorically:

- Number and percentage of subjects with the open-label extension study drug exposure  $\geq 1, \geq 14, \geq 28, \geq 42, \geq 90, \geq 120, \geq 150$  days;
- Number and percentage of subjects with the open-label extension study drug exposure for 1 13, 14 27, 28 41, 42 89, 90 119, 120 149,  $\ge 150$  days

Percent compliance will be calculated overall for the open-label extension treatment period as: (number of tablets taken / number of tablets should have been taken)  $\times$  100%. Non-compliance is defined as less than 75% or more than 125% non-missing compliance for the open-label extension treatment period. Subjects with missing compliance will not be classified as non-compliant. Percent compliance will be summarized both as a continuous variable and

categorically (ie, number and percentage of subjects in each compliance category: < 75%, 75% - 125%, > 125%, and missing).

Mean daily dose will be calculated for the entire open-label extension treatment period as the cumulative dose (mg) of SEP-363856 divided by the duration of exposure (in days), where cumulative dose is the sum of all doses a subject received during the open-label extension treatment period. Modal daily dose will be determined as the daily dose that is taken for the most time (in terms of number of days) among all doses taken. Both mean daily dose and modal daily dose will be summarized.

# 15.3.3. Important Protocol Deviations

Important protocol deviations (IPDs) will be identified and documented based on reviews of data listings and the protocol deviations log. The IPD categories may include, but may not be limited to:

- Did not satisfy important inclusion and/or exclusion criteria
- Received prohibited medication
- Overall compliance rate < 75% or > 125%.

IPDs will be identified for all enrolled subjects and presented in a data listing. The number and percentage of subjects within each IPD category will be summarized for the safety population.

#### 15.3.4. Demographic and Baseline Characteristics

Demographic and baseline characteristics data will be summarized for the safety population. Selected data (eg, PANSS total score, CGI-S score, etc.) will be summarized at both the preswitch (PS) Baseline of Study SEP361-308 and the open-label extension (OLE) Baseline of Study SEP361-309.

Medical history data collected at the entry into studies SEP361-308 will be summarized for the safety population by presenting the number and percentage of subjects with at least one condition in each system organ class (SOC) and preferred term (PT). Psychiatric history data collected at the entry into Study SEP361-308 will also be summarized for the safety population.

#### 15.3.5. Effectiveness Analyses

Effectiveness data will be summarized descriptively for the safety population.

The observed values of PANSS total score and subscale scores (positive, negative, and general psychopathology), PANSS Marder Factor (five-factor) scores, Uncorrelated PANSS (seven-factor) Score Matrix (UPSM), CGI-S score, CGI-I, BNSS total score, SF-12 score, PSP score, and MSQ score, at the PS Baseline, OLE Baseline, and each scheduled post-OLE Baseline extension visit, including the Week 24 last-observation carried forward (LOCF) endpoint, will be summarized descriptively. Changes from Baseline in these efficacy measures will be summarized at each scheduled post-OLE Baseline extension visit and Week 24 LOCF endpoint, based on both the PS Baseline and the OLE Baseline.

PANSS total score and CGI-S score data will also be summarized by age, sex, race, number of prior hospitalizations for treatment of schizophrenia, duration of schizophrenia, geographic region, and country.

The proportion of subjects who achieve a response, defined as a 20% or greater improvement (ie, decrease) in PANSS total score from the Baseline, will be calculated for each scheduled visit and the Week 24 LOCF endpoint based on the PS Baseline of study SEP361-308.

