Switching between antipsychotic medications is common in the treatment of schizophrenia (Faries-2009). There may be many reasons for switching antipsychotic treatment, including unsatisfactory response to current treatment, poor tolerability, comorbid physical and psychiatric conditions, and patient request. Clinically warranted switches can provide benefits by enhancing treatment effectiveness, tolerability, and overall acceptance by patients (Weiden-2003). Studies have shown that up to one-third of outpatients with schizophrenia in the United States switch antipsychotic therapy within one year (Weiden-2006, Buckley-2007). According to most empirically based criteria (Kinon-2000), successful switching paradigms involve gradual discontinuation of the original antipsychotic drug upon initiation of the new treatment. Individual patient characteristics, as well as the binding profile and dose level of the original antipsychotic, can influence the appropriate duration for successful discontinuation (Buckley-2007; Cerovecki-2013; Takeuchi-2018).

In light of the novel mechanism of action of SEP-363856, it is important to understand the safety and effectiveness by which a patient can be switched to SEP-363856 using common methods employed in a clinical outpatient setting.

Therefore, the current 24-week study is an open-label extension to an 8-week, outpatient, multicenter, flexible-dose, single-group study designed to evaluate the effectiveness, safety, and tolerability of switching clinically stable outpatients with schizophrenia, who can potentially benefit from a switch for tolerability or efficacy reasons, from their pre-switch antipsychotic medication to SEP-363856. The open-label extension will provide additional, long-term safety, tolerability and effectiveness data from subjects who completed the 8-week switch trial.

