# 11.4.1. Positive and Negative Syndrome Scale (PANSS)

The PANSS is an interview-based measure of the severity of psychopathology in adults with psychotic disorders. The measure is comprised of 30 items and 3 subscales: the Positive subscale assesses hallucinations, delusions, and related symptoms; the Negative subscale assesses emotional withdrawal, lack of motivation, and similar symptoms; and the General Psychopathology subscale addresses other symptoms such as anxiety, somatic concern, and disorientation. An anchored Likert scale from 1 - 7, where values of 2 and above indicate the presence of progressively more severe symptoms, is used to score each item. Individual items are then summed to determine scores for the 3 subscales, as well as a total score. A Composite scale score (Positive scale score minus Negative scale score) can also be calculated to show the relative valence of positive and negative symptoms. Total time required for the PANSS interview and scoring is approximately 30 to 40 minutes (Kay-1994, Opler-1992; Perkins-2000). The PANSS requires input from an informant (eg, caregiver, relative, friend, case worker, or hospital staff). PANSS interviews will be audio recorded and the recording may be reviewed by Sponsor's designee to monitor the quality of the rater interviews, where allowed by local/regional regulations. No identifying information will be associated with the audio recording. PANSS raters will be required to meet specific training and education criteria before they are certified to rate for this study.

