#### 11.4.4. Brief Negative Symptom Scale (BNSS)

The BNSS is a rating scale to measure the current level of severity of negative symptoms in schizophrenia and schizoaffective disorder (Kirkpatrick-2011). The measure is comprised of 13 individual items and 6 subscale scores (blunted affect, alogia, avolition, anhedonia, asociality, and distress). The 6 subscale scores provide a summary score and the 13 individual items provide a composite total score (ranging from 0 to 78). Each of the items are scored on a Likert-type 7-point scale from 0 - 6, where values of 0 indicates symptom is absent and a value of 6 means the symptom is a severe form. The number of items varies per subscale. BNSS raters will be required to meet specific training and education criteria before they are certified to rate for this study.

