## 15.3.5.3. Adjustment for Multiplicity

Not applicable as only descriptive statistics for effectiveness parameters will be compiled.

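### PANSS response is a 20% fall in a total that cannot go below 30, so the same label demands 40% of the above-floor score at a baseline of 60 and 27% at 120

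*Protocol*

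**What the plan says.** Section 15.3.5 (Effectiveness Analyses) defines PANSS response as "defined as a 20% or greater improvement (ie, decrease) in PANSS total score from the Baseline". The proportion of responders "will be calculated for each scheduled visit and the Week 24 LOCF endpoint based on the PS Baseline of study SEP361-308". So the section fixes the score, the direction, the cut-off and the reference baseline.

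Section 11.4.1 describes the scale: "The measure is comprised of 30 items and 3 subscales". Each item uses "An anchored Likert scale from 1 - 7, where values of 2 and above indicate the presence of progressively more severe symptoms", and "Individual items are then summed to determine scores for the 3 subscales, as well as a total score". No section subtracts the minimum score or rescales the items to start at 0.

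Section 15.3.5.3 states that "only descriptive statistics for effectiveness parameters will be compiled", so the response proportion is a summary and not a test. It does not appear in the endpoint lists of section 6.

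**The concern.** A percentage change is meaningful as a proportion only if the score has a true zero. The PANSS total as described here does not: complete absence of symptoms scores 30. The lower the baseline, the larger the part of the total that is floor and cannot be lost. The 20% criterion is therefore hardest to meet for mildly ill subjects and easiest for severely ill ones.

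This bears on the population at hand. Section 4.2 describes the parent study as "switching clinically stable outpatients with schizophrenia, who can potentially benefit from a switch for tolerability or efficacy reasons". That is not an acutely ill sample, so low to moderate baselines are plausible, and the distortion grows as the baseline falls. The response proportion would then reflect the baseline mix as well as improvement, and the label would suggest a uniform one-fifth reduction in symptoms. Comparing the proportion with that of a more severely ill sample would carry the same problem.

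By contrast, the BNSS in section 11.4.4 is scored "where values of 0 indicates symptom is absent", so a percentage of its total would not have this difficulty. The protocol plans no percentage rule for the BNSS, so this only illustrates the difference in scoring.

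**Working it through.** **Inputs.** From section 11.4.1: 30 items, item minimum 1, item maximum 7, simple sum. From section 15.3.5: a decrease of at least 20% from PS Baseline. The baselines B below are assumptions, since the protocol gives no PANSS baseline. The protocol also gives no expected response rate, so there is no derived figure to reproduce first.

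**Floor.** 30 × 1 = 30. The maximum is 30 × 7 = 210.

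**What the rule requires.** As written, a responder must lose 0.2B points. The score that can be lost is B − 30. The required share of it is 0.2B/(B − 30). With 30 subtracted and the cut-off kept at 20%, the requirement is 0.2(B − 30) = 0.2B − 6 points.

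| PS Baseline | Points needed as written | Above-floor score | Share that must be lost | Points needed with 30 subtracted |
|---|---|---|---|---|
| 50 | 10 | 20 | 50.0% | 4 |
| 60 | 12 | 30 | 40.0% | 6 |
| 70 | 14 | 40 | 35.0% | 8 |
| 80 | 16 | 50 | 32.0% | 10 |
| 90 | 18 | 60 | 30.0% | 12 |
| 100 | 20 | 70 | 28.6% | 14 |
| 120 | 24 | 90 | 26.7% | 18 |

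**Reversal of order.**

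- From 60 to 49: raw fall 11/60 = 18.3%, a non-responder; above-floor loss 11/30 = 36.7%.
- From 120 to 96: raw fall 24/120 = 20.0%, a responder; above-floor loss 24/90 = 26.7%.

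The first subject loses the larger share of the symptom score and is classed as the failure.

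**Where response is impossible.** The largest possible raw fall is (B − 30)/B, which equals 20% at B = 37.5. At 37, falling to the floor is 7/37 = 18.9%, so even full remission is a non-response. At 38 it is 8/38 = 21.1%, while one point short of the floor is 7/38 = 18.4%, so only full remission counts. Such baselines are probably rare.

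**Where the two scales agree.** A corrected cut-off of 30% asks for the same points as the raw 20% when 0.3(B − 30) = 0.2B, that is at B = 90, where both ask for 18.

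**The case against.** **The SAP may settle it.** Section 15 leaves statistical details to the SAP, and section 15.3.5 never uses the word raw. A SAP could subtract 30, and the one for this trial is not at hand. But the protocol does not leave a gap here: its rule can be applied as it stands, and applied literally it uses the unadjusted total. Subtracting 30 would change the rule and not merely add detail to it, so the protocol text should say which is meant in either case.

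**The consequence is small.** This stands. Response is not a listed endpoint, effectiveness is descriptive, and with a single treatment group no between-arm comparison can be biased. PANSS totals are summarised at both baselines (section 15.3.4), and observed values and changes are summarised at every scheduled visit with the scale. A careful reader can see the baseline level and the point changes, though not how they enter the proportion.

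**The reversal depends on the metric.** In points, the fall from 120 to 96 is the larger (24 against 11), so the rule agrees with the absolute ordering. That is true, but the protocol chose a proportional criterion, and a proportional criterion needs a true zero.

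**The spread depends on assumed baselines.** This also stands. Between 70 and 100 the required share runs only from 35% to 28.6%, and no effect on the actual proportion can be shown without data.

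**The correction is more lenient.** Keeping 20% after subtracting 30 lowers the bar by 6 points at every baseline, and in an uncontrolled study the wording as written is the stricter of the two. This is correct. It is the reason to print both proportions and not to replace one by the other.

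**Conclusion.** The concern holds. On the protocol's own description of the scale, the response rule asks for a share of the above-floor score that falls from 50% at a baseline of 50 to 26.7% at 120. It can class the larger proportional improvement as non-response, and it cannot be met at all from a baseline of 31 to 37.

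The floor of 30 and the formulas follow from the document. What is assumed is the baseline range, and with it how much the distortion matters in this sample. The effect is confined to how one descriptive proportion is read and compared. The change is worth making because it costs little, not because any main conclusion depends on it.

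**What to change.** In section 15.3.5, define percent improvement as 100 × (PS Baseline − visit score)/(PS Baseline − 30), set to not evaluable if PS Baseline is 30. Report the proportion with at least 20% improvement on this scale. Print the proportion under the uncorrected rule beside it, and label each with its formula.

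The cost is one formula and one extra table row, on data already collected. The drawback should be stated with the table: the corrected 20% rule needs 6 fewer points at every baseline before rounding (6 against 12 at 60; 10 against 16 at 80). Its rate will be the same or higher and must not be compared with uncorrected rates from other studies.

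The cut-off on the corrected scale is a separate choice. A further row for at least 30% improvement, which matches the raw rule at a baseline of 90, would show how lenient 20% is once the floor is removed.
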